19.2.2 Figure Outlines

Template F_PK1

Figure 14.2.xx Individual 5-MeO-DMT plasma concentration-time plots (linear and semi-log)

[figure not shown]

Source: Listing 16.2.xx

Programming notes: Page by treatment and include all Patients on same page

Template F_PK2

Figure 14.2.xx Mean (+/- SD) 5-MeO-DMT plasma concentration-time plots (linear and semi-log)

[figure not shown]

Source: Listing 16.2.xx

BLQ values are imputed to zero

Template F_PD

Figure 14.2.xx Individual mean units of alcohol per day (UPD)-time plots [intent-to-treat population]

[figure not shown]

Source: Listing 16.2.xx

Programming notes: Include all Patients with a patient legend

Template F_SAF1

Figure 14.3.1 Individual systolic blood pressure-time plots

Source: Listing 16.xx

Programming note: Continue with all parameters
Update the x-axis label to "Planned Relative Time"

19.2.3 Listing Outlines

Template L_SD1_PG

Listing 16.2.x.xx Listing of study dates

Treatment	Patient	Screening	Day 0	Follow Up		
				Day 1	Day x	Day 84

Programming notes: Lists dates for screening, dosing Day and follow up days
If a repeat screening was done, report the original and if a repeat FU was done, report the repeat FU

Template L_SD2_PG

Listing 16.2.x.xx Listing of reasons for withdrawal

Treatment	Patient	Date of Withdrawal	Study Day	Reason
-----------	---------	--------------------	-----------	--------

Programming notes: Reason for withdrawal is concatenation of reason and details

Template L_SD3_PG

Listing 16.2.x.xx Listing of patients screened but not enrolled

Screen Number	Date of Screen	Failure Category	Details
---------------	----------------	------------------	---------

Template L_TD1_PG

Listing 16.2.x.xx Listing of patients with time deviations

Treatment	Patient	Planned Relative Time	Procedure	Allowed deviation (h:min)	Actual deviation (h:min)	Time outside the deviation window (h:min)
-----------	---------	-----------------------	-----------	---------------------------	--------------------------	---

Programming notes: Only include time deviations which exceed the allowed deviation

Template L_DV2_PG

Listing 16.2.x.xx Listing of patients with minor protocol deviations

Treatment	Patient	Protocol Deviation	Type of Deviation
-----------	---------	--------------------	-------------------

Programming notes: Protocol deviation is in the form "Time x: DVTERM". Separate listing for minor and major protocol deviations

Template L_AN1_PG

Listing 16.2.x.xx Listing of analysis populations

Treatment	Patient	Safety Population	Population 1	Population 2
-----------	---------	-------------------	--------------	--------------

Template L_DM1_PG

Listing 16.2.x.xx Listing of demographic characteristics

Treatment	Patient	Date of visit	Year of birth	Age (y)	Sex	Race	Ethnicity	Height (cm)	Weight (kg)
↓	↓								

Programming notes: Continued with all patients and other demographic characteristics. Include baseline weight and height

Template L_CM1_PG

Listing 16.2.x.xx Listing of concomitant medications

Treatment	Patient	Medication Class/ Medication Code*	Drug Name/ Indication	Dose/ Freq/Route	Date/time Started/ Date Stopped	Study Day Started/ Time Since Last Dose	Started Pre- Dose?	Ongoing Medication?
-----------	---------	---------------------------------------	--------------------------	---------------------	------------------------------------	---	-----------------------	------------------------

*Coded using WHODrug Global vXX.X

Programming notes: Include dose and units (e.g. 5 mg)/Freq/Route

Template L_MH1_PG

Listing 16.2.x.xx Listing of medical history

Treatment	Patient	Category	System organ class*/Preferred term	Verbatim text	Clinical significance	Date Started	Date Stopped	End relative to Screening
-----------	---------	----------	---------------------------------------	---------------	--------------------------	-----------------	-----------------	------------------------------

*Coded using MedDRA vXX.X

Template L_AUH_PG

Listing 16.2.x.xx Listing of alcohol use history data

Treatment	Patient	Date of Admission for Treatment of Current AUD Episode	Age Drinking Problem Recognised	AUD DSM-V Score	AUD Severity (number of DSM-V Symptoms)	Abstinence Details
-----------	---------	---	------------------------------------	-----------------	---	-----------------------

AUD= Alcohol use disorder

Template L_DUH_PG

Listing 16.2.x.xx Listing of drug abuse use history data

Treatment	Patient	Drug Type Used in Lifetime	Result
		Drug 1	Yes
		Drug 2	Yes
		etc	Yes

Programming notes: Continued with all drug types. Only list where Result is "Yes"

Template L_EX1_PG

Listing 16.2.x.xx Listing of exposure data

Treatment	Patient	Start Date/ Start Time of Dose	Dose	Dose Unit	Formulation/ Route	Frequency
Treatment 1	1001	01JAN2002/23:59	25	mg	Tablet/ Oral	Once

Template L_PK1_PG

Listing 16.2.6.xx Listing of 5-MeO-DMT and bufotenine plasma pharmacokinetic concentration-time data

Treatment	Patient	Date	Planned Relative Time	Actual time (hh:mm)	Time Deviation (min)	Actual Relative Time (h)	Concentration (units)			
							5-MeO-DMT	Bufotenine	5-methoxyindolacetic acid	5-MeO-DMT-N- Oxide

Below the Limit of Quantification (BLQ) is < xx units for 5-MeO-DMT, < xx units for bufotenine, < xx units for 5-methoxyindolacetic acid and < xx units for 5-MeO-DMT-N-Oxide

Programming notes: Values below LLOQ are shown as BLQ. Check LLOQ value in final PK spreadsheet for each analyte.

Template L_PD1_PG

Listing 16.2.x.xx Listing of Stanford Expectation of Treatment Scale

Treatment	Patient	Planned Relative Time	Date/Time	Positive expectancy	Negative expectancy
		Time 1	26SEP2012:09:57	x	x

Template L_PD2_PG

Listing 16.2.x.xx Listing of Mystical Experience Questionnaire (MEQ-30)

Treatment	Patient	Planned Relative Time	Date/Time	Mystical Subdomain	Positive Mood Subdomain	Transcendence of Time and Space Subdomain	Ineffability Subdomain	Total MEQ Score
		Time 1	26SEP2012:09:57	x	x	x	x	x

Template L_PD3_PG

Listing 16.2.x.xx Listing of Ego Dissolution Inventory (EDI)

Treatment	Patient	Planned Relative Time	Date/Time	Question 1	Question x	Total EDI Score	Comment
		Time 1	26SEP2012:09:57	x			

Programming note: Total EDI Score only required for EDI

Template L_PD4_PG

Listing 16.2.x.xx Listing of Stanford Expectation of Treatment Scale (SETS)

Treatment	Patient	Planned Relative Time	Date/Time	Positive expectancy	Negative expectancy	What treatment are you going to receive?	Specific benefits you expect to receive?	Specific harms or negative side-effects you think may occur?	Have you ever received this treatment?
		Day -12	26SEP2012/09:57	x.xx	x.xx	xxxxxxxxxxx	xxxxxxxxxxx	xxxxxxx	No

Template L_PD4a_PG

Listing 16.2.x.xx Listing of Montgomery-Åsberg Depression Rating Scale (MADRS)

Treatment	Patient	Planned Relative Time	Date/Time	Total MADRS Score	Etc.
		24 H	26SEP2012/09:57	x	

All questionnaire programming notes: Include columns for all scores (total and/or average score) for all questionnaires (where applicable) as described in Appendix A.

Template L_PD5_PG

Listing 16.2.x.xx Listing of 5-Level EuroQol 5-Dimension (EQ-5D-5L)

Treatment	Patient	Planned Relative Time	Date/Time	Mobility					Self-care		etc
				I have no problems in walking about	I have slight problems in walking about	I have moderate problems in walking about	I have severe problems in walking about	I am unable to walk about	I have no problems washing or dressing myself	I have slight problems washing or dressing myself	
		24 H	26SEP2012/09:57	x	x	x	xx		x	x	

Programming notes: Continued with all Items assessed including the VAS "How good or bad your health is today (mm)" and time points.

Template L_PD6_PG

Listing 16.2.x.xx Listing of Timeline Follow-Back (TFLB)

Treatment	Patient	Longest continuous number of abstinence (days)	Max number of standard units of alcohol consumed on any one day					Number of Heavy Drinking Days (HDD)					Number of days after dosing to first drink	Number of days after dosing to first HDD	Average number of standard units of alcohol consumed per week				
			85 Days Prior Day-3	Day 14	Day 28	Day 56	Day 84	85 Days Prior Day-3	Day 14	Day 28	Day 56	Day 84			85 Days Prior Day-3	Day 14	Day 28	Day 56	Day 84
		x	x	x	x	x	x	x	x	x	x	x			x	x	x	x	x

listing continued

Treatment	Patient	Percentage of Heavy Drinking Days (PHDD)					Percentage of Drinking Days (PDD)					Mean Units per Day (UPD)					Abstinence: Percentage of Abstinent Days (PAD)				
		85 Days Prior Day-3	Day 14	Day 28	Day 56	Day 84	85 Days Prior Day-3	Day 14	Day 28	Day 56	Day 84	85 Days Prior Day-3	Day 14	Day 28	Day 56	Day 84	85 Days Prior Day-3	Day 14	Day 28	Day 56	Day 84
		x	x	x	x	x	x	x	x	x	x	x	x	x	x	x	x	x	x	x	x

Note: 85 Days Prior Day -3 = 85 Days Prior Day -3 (or start of detox)

Template L_PD7_PG

Listing 16.2.x.xx Listing of Alcohol Craving Questionnaire (ACQ)

Treatment	Patient	Planned Relative Time	Date/Time	Question 1	Question 2	Etc.
		Time 1	26SEP2012:09:57	x		

Template L_PD8_PG

Listing 16.2.x.xx Listing of Clinical Global Impression-Severity (CGI-S)

Treatment	Patient	Planned Relative Time	Date/Time	Considering your total clinical experience with this patient population, how ill is the patient at this time?
		Time 1	26SEP2012/09:57	0

Programming notes: For PGIC use "Since the start of the study, my overall status is"

Template L_PD9_PG

Listing 16.2.x.xx Listing of Clinical Institute Withdrawal Assessment for Alcohol- Revised (CIWA-Ar)

Treatment	Patient	Planned Relative Time	Date/Time	Nausea and vomiting	Tremor	Paroxysmal Sweats	Etc.
		Time 1	26SEP2012:09:57	x	x	x	x

Template L_AE1_PG

Listing 16.2.x.xx Listing of all adverse events

Treatment	Patient	System Organ Class* / Preferred Term/ Verbatim Text	Outcome/ Onset Date/Time/ Resolved Date/Time/ Duration	Study Day Started/ Time Since Last Dose	Severity/ Serious/ Withdrawal/AESS/ AESI	Frequency/ Action Taken (1)/ Other Action Taken	Related to Study Drug/ Treatment Emergent?
Treatment 1	1001	Gastrointestinal Disorders / Intestinal Spasm / Entero-spasm	Resolved/ 24SEP2003 13:05/ 27OCT2003 7:50/ 34d 4h 5m	Day x/ 10d 7h 3m	Mild/ No/ Yes	Intermittent/ Dose not changed/ None	Possibly/ Yes

(1) Action Taken with Study Treatment

*Coded using MedDRA vXX.X

AESS = Adverse event of special situation

AESI = Adverse event of special interest

Programming notes: For the listing of "other significant AEs" include (from ICH E3) AEs leading to withdrawal, AEs leading to dose reduction (including drug withdrawn, interrupted, reduced or similar) and AEs with AEOSE=Y. If AEOSE has not been collected then use "Otherwise significant" in the CRF.

Template L_LB1_PG

Listing 16.2.x.xx Listing of post dose clinically significant abnormal chemistry laboratory values

Treatment	Patient	Laboratory test (units)	Planned Relative Time	Date/Time	Value	Clinically Significant?
Treatment 1	1001	XXX	Time 1	01JAN2002/13:34		
			Time 2	01APR2002/09:22		Y

Programming notes: Lists only patients with clinically significant post-dose results. Alcohol biomarkers, include CDT and Urine EtG

Template L_VS1_PG

Listing 16.2.x.xx Listing of vital signs of potential clinical importance

Treatment	Patient	Planned Relative Time	Date/Time	Systolic Blood Pressure (mmHg)	Diastolic Blood Pressure (mmHg)	Etc (units)
		24 H	26SEP2012:09:57	63	148*	

* Value of potential clinical importance

Template L_VS2_PG

Listing 16.2.x.xx Listing of clinically significant vital signs

Treatment	Patient	Planned Relative Time	Date/Time	Vital Sign Finding	Comment on Clinical Significance
-----------	---------	-----------------------	-----------	--------------------	----------------------------------

Programming notes: Lists only values with abnormal CS

Template L_VS3_PG

Listing 16.2.x.xx Listing of peak vital signs data

Treatment	Patients	Planned Relative Time	Systolic Blood Pressure (mmHg)	Diastolic Blood Pressure (mmHg)	Heart Rate (beats/min)
		Predose	160	148	50
		Day 0, Postdose	163	148	55

Programming notes: Continued with all treatments and subjects. List only the maximum value

Template L_EG1_PG

Listing 16.2.x.xx Listing of QTcF values of potential clinical importance

QTcF (msec)									
Treatment	Patient	Planned	Date/Time	Heart	QRS		QRS		Change
		Relative Time		Rate	PR Int.	Dur.	Axis	QT Int.	from
				(bpm)	(msec)	(msec)	(deg)	(msec)	Observed Baseline
		24 H	26SEP2012:09:57	63	148	78	50	390	396 -6.5

* Value of potential clinical importance

Template L_EG2_PG

Listing 16.2.x.xx Listing of abnormal ECG findings

Treatment	Patient	Planned Relative Time	Date/Time	ECG Finding	Comment on Clinical Significance
-----------	---------	-----------------------	-----------	-------------	----------------------------------

Programming notes: Lists only abnormal values or values with comment on ECG result
ECG Finding contains Physician's Opinion from CRF and relates to whole trace (not individual parameters), e.g. Normal, Abnormal - NCS or Abnormal - CS

Template L_EG3_PG

Listing 16.2.x.xx Listing of abnormal cardiac telemetry findings

Treatment	Patient	Start Date/Start Time	End Date/End Time	Telemetry Finding	Comment on Clinical Significance
				Abnormal - CS	

Programming notes: Lists only abnormal values or values with comment on telemetry result. Telemetry findings will be in the form Normal, Abnormal - NCS or Abnormal - CS

Template L_PE1_PG

Listing 16.2.x.xx Listing of abnormal physical examination findings

Treatment	Patient	Planned Relative Time	Date	Site	Details
-----------	---------	-----------------------	------	------	---------

Programming Notes: List only findings with an 'abnormal' result. Details contains Details concatenated with NCS or CS
If patients have multiple abnormal sites at a given time, create a separate row for each site.

Template L_NSE1_PG

Listing 16.2.x.xx Listing of abnormal nasal site and throat examination findings

Treatment	Patient	Planned Relative Time	Date/Time	Site	Details	Irritancy Score
-----------	---------	-----------------------	-----------	------	---------	-----------------

Programming Notes: List only findings with an 'abnormal' result. Details contains Details concatenated with NCS or CS
If patients have multiple abnormal sites at a given time, create a separate row for each site.

Template L_CSS_PG

Listing 16.2.x.xx Listing of positive columbia-suicide severity rating scale data

Treatment	Patient	Planned Relative Time	Date/Time	Question	Category	Result
-----------	---------	-----------------------	-----------	----------	----------	--------

Template L_RDQ_PG

Listing 16.2.x.xx Listing of readiness for discharge questionnaire (RDQ)

Treatment	Patient	Planned Relative Time	Start Date/Time	End Date/Time	Question	Result
	1001	Time 1	26SEP2012:09:52:20	26SEP2012:09:54:20	The patient is fully responsive	No
					The patient is fully responsive	Yes
					Acute psychedelic effects have subsided	Yes
					The patient is fully orientated	Yes
					Blood pressure/pulse rate are normal	Yes
					Patient has stable gait can walk safely	Yes
					Side effects are mild/moderate intensity	Yes
					No acute suicidal ideations/intentions	Yes
					Feelings of being overwhelmed have gone	Yes
					The patient is now safe to be discharged	Yes
					Time to discharge (hours)	2.3

Note: Time to discharge is defined as time when all criteria are met

Programming Notes: Continued with all questions. Calculate time to discharge from the end time and report as last row

Template L_ReAQ_PG

Listing 16.2.x.xx Listing of re-activation questionnaire (ReAQ)

Treatment	Patient	Planned Relative		Occurrence	Date of event?	No. of Days after dose	No. of Re-activations	Functional Impact				
		Time	Date/Time					Emotional Valence	Work	Life	Family Life	Narrative
				Yes	26SEP2012	5	2	Mostly Positive	Mild	Mild	Moderate	xxxx
				No								

19.3 Table of footnotes for data display specifications (questionnaires only)

Listing/Table Number	Description	Footnotes
16.2.6.2	Listing of Stanford Expectation of Treatment Scale	SETS is a 10 item scale with 6 items used to calculate expectancy
16.2.6.3	Listing of Mystical Experience Questionnaire (MEQ-30)	Total MEQ-30 Score = (Mystical Subdomain + Positive Mood Subdomain+ Transcendence Subdomain + Ineffability Subdomain) / 4 A 'complete mystical experience' is defined as a patient scoring 3 or more on each of the four subdomains.
16.2.6.4	Ego-Dissolution Inventory (EDI)	The EDI is an 8-item measure which will be used to measure the acute ego dissolution experience during dosing using visual analogue scale (VAS) from 0 ('No, not more than usually') to 100 ('Yes, entirely or completely'). Total score is calculated as mean of all 8 items.
16.2.6.12	Clinical Institute Withdrawal Assessment for Alcohol-Revised (CIWA-Ar)	The maximum score is 67; mild alcohol withdrawal is defined by a score ≤ 10 , moderate by scores 11 to 15, and severe by any score ≥ 16 .

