The active metabolite, bufotenine, was only detected at very low levels (1.46ng/mL), at the 6 mg dose level 16 min timepoint in one study participant.

In this study assessments were made of PD endpoints that were thought to be predictive of efficacy outcomes in TRD subjects. Literature data indicate that the 30-item Mystical Experience Questionnaire (MEQ-30) data may be used as a surrogate marker of potential future psychiatric efficacy ([Hirschfield, 2021](#); [Griffiths, 2011](#)), and so was the key PD outcome measure conducted. A score of ≥ 3 was defined to be the threshold to elicit a significant experience. A score of ≥ 3 in all 4 subdomains of the MEQ-30 was defined as a complete mystical experience (Barrett, 2015).

The mean subject MEQ-30 scores generally increased with BPL-003 dose, with levels ≥ 3 being observed at doses of 6 mg and above in at least one sub-domain or total MEQ-30 score. The highest MEQ-30 scores were attained with 12 mg BPL-003, and 3 of 5 subjects (60%) achieved a complete mystical experience at 10 mg and 12 mg doses.

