2.2 Analysis and reporting

Factor scores are computed by calculating the mean response to the following items:

- Mystical items are: 4, 5, 6, 9, 14, 15, 16, 18, 20, 21, 23, 24, 25, 26, 28.
- Positive mood items are: 2, 8, 12, 17, 27, 30.
- Transcendence items are: 1, 7, 11, 13, 19, 22.
- Ineffability items are: 3, 10, 29.

The MEQ30-total score is computed by taking the mean response to all items.

3 Ego Dissolution Inventory (EDI)

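### The SAP defines the MEQ-30 total score in two incompatible ways: the mean of all 30 items in Appendix A, and the unweighted mean of four unequal subdomains in the Section 19.3 footnote

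*SAP*

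**What the plan says.** SAP Appendix A, section 2.2, scores the MEQ-30. On the subdomains it says "Factor scores are computed by calculating the mean response to the following items", and it then assigns every item to one of four lists. The longest list has 15 entries ("Mystical items are: 4, 5, 6, 9, 14, 15, 16, 18, 20, 21, 23, 24, 25, 26, 28"), while the shortest has only three ("Ineffability items are: 3, 10, 29"). The lists for positive mood and transcendence have six entries each.

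On the total it says "The MEQ30-total score is computed by taking the mean response to all items".

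SAP Section 19.3 gives footnotes for the questionnaire displays. The one for Listing 16.2.6.3 reads "Total MEQ-30 Score = (Mystical Subdomain + Positive Mood Subdomain+ Transcendence Subdomain + Ineffability Subdomain) / 4".

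The listing template (L_PD2_PG) has a column for each of the four subdomains and one for the total. The table of contents in SAP Section 19.1 names this listing as the source for Tables 14.2.3.1 (ITT) and 14.2.3.2 (PP), which summarise the MEQ-30 using template T_PD1. The effects of BPL-003 as measured by the MEQ-30 and EDI are a secondary endpoint (Protocol 3.2, SAP 4.2.2).

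**The concern.** Both formulas are averages and look alike, but they agree in general only if the four subdomains have the same number of items, which they do not. Because Appendix A builds the subdomain scores as means and not sums, the footnote cannot be read as the item mean in other notation.

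At stake is the consistency of one reported score. Either the listing is computed from the footnote and disagrees with the tables drawn from it, or it is computed from Appendix A and printed above a formula that does not produce its values. The study tests no hypotheses (SAP 4.3), so the descriptive figures are the result. The study is also open-label, with ongoing sponsor review of data (SAP 7.1). A score with two written definitions leaves a choice that could be made after the data have been seen.

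**Working it through.** The plan states no figure to reproduce, so the check compares the two formulas directly.

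**Inputs.** The item lists in Appendix A, section 2.2, contain 15 (mystical, M), 6 (positive mood, P), 6 (transcendence, T) and 3 (ineffability, I) items. 15 + 6 + 6 + 3 = 30, and each item from 1 to 30 appears exactly once. Items are scored 0 to 5 (Appendix A, section 2.1).

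**Formulas**, with M, P, T and I as subdomain means:

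- Appendix A: (15M + 6P + 6T + 3I)/30 = 0.50M + 0.20P + 0.20T + 0.10I
- Footnote: (M + P + T + I)/4 = 0.25M + 0.25P + 0.25T + 0.25I
- Appendix A minus footnote: 0.25M − 0.05P − 0.05T − 0.15I

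The difference is zero only when 5M = P + T + 3I, for example when all four subdomain means are equal. Under the footnote, ineffability counts 0.25/0.10 = 2.5 times as much and the mystical subdomain half as much.

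**Worked profiles** (illustrative, not trial data):

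| M, P, T, I | Appendix A | Footnote | Footnote minus Appendix A |
|---|---|---|---|
| 3, 3, 3, 3 | 90/30 = 3.00 | 12/4 = 3.00 | 0 |
| 2.4, 3.0, 3.5, 4.0 | (36 + 18 + 21 + 12)/30 = 2.90 | 12.9/4 = 3.225 | +0.325 |
| 3, 4, 4, 5 | (45 + 24 + 24 + 15)/30 = 3.60 | 16/4 = 4.00 | +0.40 |
| 4, 3, 3, 2 | (60 + 18 + 18 + 6)/30 = 3.40 | 12/4 = 3.00 | −0.40 |
| 0, 5, 5, 5 | 75/30 = 2.50 | 15/4 = 3.75 | +1.25 |
| 5, 0, 0, 0 | 75/30 = 2.50 | 5/4 = 1.25 | −1.25 |

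The second profile is attainable with whole-number answers: its item sums are 36, 18, 21 and 12.

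**Largest gap.** In the difference the coefficient on M is +0.25 and the other three sum to −0.25. On a 0-5 scale the maximum is therefore 0.25 × 5 = 1.25, reached only at the last two profiles.

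**Typical gap.** The documents give no MEQ-30 subdomain data from which to estimate it. An illustrative simulation of 200,000 patients, assuming independent uniform answers from 0 to 5 on every item, gave equal totals in 1.7% of cases and a mean absolute gap of 0.15. That assumption is not a model of real responses.

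**Group means.** Both formulas are linear, so the gap between group mean totals is the same expression applied to the group mean subdomain scores. If patients share a profile, the gap does not average out.

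**The case against.** The strongest reply is that the SAP already points to Appendix A for scoring. Section 16 says each scale is reported as Appendix A describes. The T_PD1 programming note refers to Appendix A for the subscales. The general questionnaire note in the listing templates does so for total and average scores. Section 19.3 is only a table of display footnotes, so the likeliest outcome is a wrong footnote and not two computed totals. This largely stands and it settles the direction of the fix. It does not remove the inconsistency: no clause ranks the two sections, the T_PD1 note mentions subscales only, and a programmer could code the formula printed for the listing.

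The reach is also narrow. The total is one of five MEQ-30 scores. Up to 12 patients are planned and no primary or safety output is involved. The listing shows the four subdomain scores beside the total, so a reader could recompute either version, up to rounding. All of this stands.

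Two stronger readings are tempting. One is that a patient's classification could change, because 2.90 and 3.225 fall on either side of 3. Protocol 1.4.2.3.1 does say that a score of 3 or more "was defined to be the threshold to elicit a significant experience", but that describes the Phase 1 study. No output in this SAP divides patients by their total: T_PD1 reports n, mean, SD, median, minimum and maximum. The only rule here that uses 3 is the complete mystical experience, which applies it to each subdomain. The other reading is that a comparison with Phase 1 totals would be distorted. Neither the endpoints nor the MEQ-30 outputs include such a comparison, and the documents do not say which formula Phase 1 used.

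**Conclusion.** The SAP contains two definitions of the MEQ-30 total that cannot both be right, and one must be corrected. The algebra rests only on the SAP's own item lists and on scoring subdomains as item means. Moderately uneven profiles in the table differ by 0.325 to 0.40 points; 1.25 is an upper bound and not an expected size. The gap to be seen in this trial cannot be stated from the documents.

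The effect is confined to the total in Listing 16.2.6.3 and in Tables 14.2.3.1 and 14.2.3.2. The percentage with a complete mystical experience does not change under either formula. Severity is minor to moderate: a real error in a pre-specified descriptive score within a secondary endpoint, with no test, cut-off or decision rule attached to it.

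**What to change.** Before database lock, replace the formula in the Section 19.3 footnote for Listing 16.2.6.3 with: Total MEQ-30 Score = mean of all 30 items. Keep the second sentence of that footnote, which defines the complete mystical experience. Leave Appendix A, section 2.2, unchanged. Then confirm that the total in the listing and the total in Tables 14.2.3.1 and 14.2.3.2 come from the same derivation.

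The cost in the SAP is one line. Whether any program needs changing cannot be judged from the documents. No data collection, endpoint or sample size is affected.
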